3.3 Preclinical Evidence

Not applicable.

3.4 Clinical Evidence to Date

A High-resolution OCT system uses broadband light sources to achieve axial resolutions below the 7- μm range of standard commercial OCT instruments²². Former High resolution OCTs (Spectral/Fourier Domain) often used light-sources of 840-nm center wavelength and previous studies have shown that the visualization of photoreceptor impairment, retinal pigment epithelium (RPE) disruption, drusen, which are important markers of age-related macular degeneration (AMD) progression, have been drastically improved²²⁻²⁴.

The limited imaging range of High-Resolution OCTs at 840 nm has been a substantial barrier to its clinical adoption. To achieve fine axial resolution, the OCT spectrometer should be designed to cover a broad wavelength range by compromising the spectral resolution—the wavelength difference between adjacent line-scan camera pixels. Former High-Resolution OCTs had a limited axial image range because imaging range is inversely related to spectral resolution. Thus, a High-Resolution OCT imaging requires finer transverse spatial sampling of the retina, mandating higher acquisition speeds. Complex SD-OCT have been designed to resolve this issue by using for example multiple line-scan cameras²⁵, however, sufficient depth range for reliable clinical application has not been made possible until now. To create a sufficient depth range and high spatial resolution the High-Resolution OCT uses an infrared Laser of 730 nm wavelength.

3.5 Justification for the design of the clinical investigation

The SPECTRALIS © HighRes-OCT is indicated as an aid in the visualization of structures of the retina and choroid. The SPECTRALIS © HighRes-OCT is indicated as a device to aid in the detection and management of ocular diseases including, but not limited to, macular holes, cystoid macular edema, diabetic retinopathy, hypertensive retinopathy, age-related macular degeneration, optic nerve neuropathy and glaucoma.

3.6 Explanation for choice of comparator

The comparator in this study is conventional imaging of the retina with fluorescein angiography and standard SD-OCT. The fluorescein angiography allows to image the retinal vasculature using a dye and is routinely performed in clinical routine for diagnosis of retinal vasculopathies. Fluorescein angiography (FA) and indocyanine green angiography (ICGA) are both invasive test that require intravenous administration of dye and imaging up to 10–30 minutes²⁶. The SD-OCT is used in the clinical routine and allows to image the retinal structure with an axial resolution of approximately 7 μm .

3.7 Risk evaluation (Risk-to-Benefits rationale)

This ophthalmological examination is non-invasive and is routinely performed to diagnose and monitor pathologies in eye diseases. High Resolution OCT is used in clinics (within research framework) and no adverse events have been reported. All instruments used in this study, are certified with a CE mark. The light intensities in the High-Resolution OCT are below the light levels used for a standard fluorescein angiography or autofluorescence imaging and the Optical Safety of this device conforms to IEC 60825-1, EN ISO 15004-2 and is classified as a group 1 instrument per EN ISO 15004-2 (Group 1 instruments are ophthalmic instruments for which no potential light hazard exists).

Study data will be collected in REDCap, a secure, and validated web application for building and managing online surveys and databases, in order to provide a maximum on data security. With this background, we consider from a clinical point of view that the benefits by far outweigh the risks and the study procedures (i.e. standard, routine clinical examinations) per se represent a low risk to the study participants.

3.8 Justification of the choice of the investigation population

The study population will consist of adult patients > 18 years of age with retinal diseases. The rationale for the age cut off is based on the large incidence of retinal diseases such as type I and type II diabetes mellitus or arterial hypertension. In order to validate the High-Res-OCT method we plan to analyze a subgroup of healthy subjects. Minors, participants incapable of judgment or participants under tutelage will not be included in this study.

4. CLINICAL INVESTIGATION OBJECTIVES

4.1 Overall Objective

The study aim is to investigate the diagnostic accuracy of the High-Resolution OCT in comparison with conventional imaging methods and whether High-Resolution OCT can reliably diagnose retinopathies thereby making more invasive investigations such as fluorescein angiography or conventional imaging methods futile. The main goal is to facilitate diagnosis of eye diseases for individual patients.

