The SPECTRALIS device was introduced by Heidelberg Engineering in 2006 based on the Heidelberg Retina Angiograph 2 (HRA2)^{20,21}. It incorporates two complementary imaging techniques: confocal scanning laser ophthalmoscopy (cSLO) and optical coherence tomography (OCT). The Superluminescent Diodes (SLD) has a center wavelength of 880 nm and a spectral bandwidth of 40 nm (full-width-half-maximum, FWHM), resulting in an axial resolution of approximately 7 μm in the eye. The spectral resolution of the spectrometer determines the characteristic roll-off in sensitivity with imaging depth. Compared to the first generation OCT device (40 kHz A-scan rate), the roll-off of SPECTRALIS with OCT Module has been improved considerably to less than 5 dB over an imaging depth of 1.9 mm. There is a tradeoff between acquisition speed and sensitivity: The higher the line rate, the faster the image acquisition but the less that photons can be detected. Acquisition speed therefore is inherently coupled to the sensitivity of the system. For retinal imaging, the maximum laser power is set by the exposure limit according to the laser safety guidelines. Therefore, to compensate for shorter integration time, the power can only be increased up to a limit (1.2 mW). At the same time, eye motion, heart beat and any motion in general requires accelerated acquisition.

Recently a new improvement of the OCT has been developed, the high resolution OCT, with a light-source capable of providing an increased axial resolution. The High-Res OCT works with a central wavelength of 840 nm and an increased bandwidth (130 nm), making it possible to improve the optical axial resolution in tissue from 7 to 3 μm , without increasing the maximum laser exposure limit. The improved axial resolution of the High-Res OCT results in clearer and more detailed images resolving even minuscule vessels in the retinal layers and the choriocapillaris.

The overall study aim is whether High-Res OCT can reliably diagnose retinopathies thereby making more invasive investigations such as fluorescein angiography futile and to investigate the diagnostic accuracy of the High-Res OCT in comparison with conventional imaging methods. The main goal is to facilitate diagnosis of eye diseases for individual patients.

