4.2 Primary Objective

The primary objective of this study is to evaluate the sensitivity and specificity to diagnose retinal morphological abnormalities with High-Resolution OCT compared to conventional imaging methods, such as SD-OCT, fluorescein angiography. The main parameters, which will be assessed are the presence of morphological abnormalities (such as but not limited to intraretinal or subretinal fluid, epiretinal membrane, substance defect, drusen, hyperreflective foci, atrophy, neovascularization, optic nerve, swelling, choroid abnormalities, scars, ischemia) within the macula and optic nerve head. The incidence (binary) and diagnostic accuracy of these morphological abnormalities will be assessed in High-Res-OCT and compared to conventional imaging methods such as SD-OCT.

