5. CLINICAL INVESTIGATION OUTCOMES

5.1 Primary Outcome

The primary outcome as measured on the individual patient-level is whether High-Resolution OCT has a similar or higher specificity and sensitivity to detect pathological changes in the retina/optic nerve as conventional imaging methods, such as SD-OCT, color fundus photography and fluorescein angiography. This will result in a binary outcome. Pathological morphological changes includes but are not limited to, intraretinal or subretinal fluid, epiretinal membrane, substance defect, drusen, hyperreflective foci, atrophy, neovascularization, optic nerve swelling, choroid abnormalities, scars, ischemia. Additionally, study participants will be asked to consent to prospective collection of clinical and demographic data, to correlate findings of High-Resolution OCT imaging to subsequent clinical course.

Ophthalmic diseases include, but are not limited to:

- Retinal vascular diseases
- Retinal detachment
- Hereditary retinal diseases/dystrophies
- Glaucoma
- Optic nerve neuropathy
- Inflammatory/infectious retinal diseases

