5.2 Secondary Outcomes

- Evaluation of the inter-reader reproducibility in healthy subjects with High-Res-OCT
- Evaluation whether pathological changes seen in SD-OCT or color fundus photography correlate with changes seen in High-Res-OCT. Here, a binary readout, i.e pathology present (yes/no) will be used.
- Subgroup analysis will be performed with patients suffering from diabetic retinopathy, artery and vein occlusion, retinal detachment, glaucoma, optic nerve neuropathy, hereditary retinal diseases, age related macular degeneration, retinal changes from arterial hypertension and uveitis
- Evaluation of the intra-and inter-reader reproducibility in the diagnosis (binary) using High-Res-OCT
- Evaluation of the segmentation quality of the retinal layers using High-Res-OCT. For this purpose the discrimination capacity between the different retinal layers will be assessed, especially in the healthy group. For this purpose, a binary outcome will also result.

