8.1.2 Control Intervention (standard/routine/comparator)

The routine (standard) examinations to investigate retinal pathologies are spectral-domain optical coherence tomography (SD-OCT), color fundus imaging and fluorescein angiography. These investigations are routinely performed in daily clinical practice. SD-OCT and color fundus imaging are noncontact and dye free imaging methods. Intravenous Fluorescein angiography (IVFA) is a technique for examining the circulation of the retina and choroid using a fluorescent dye and a specialized camera. The nurse will ensure intravenous access with a venflon intravenous cannulation device. Just prior to obtaining images 500 mg (1 ampoule of 5 mL) of fluorescein (Fluoresceine 10% Faure, Novartis Pharma AG, Basel, Switzerland) will be injected intravenously. Then an angiogram is obtained by photographing the fluorescence emitted after illumination of the retina with blue light at a wavelength of 490 nanometers. This test uses the dye tracing method. In daily routine patient consent is obtained to perform fluorescein angiography. If there is known hypersensitivity or allergy to fluorescein no fluorescein angiography is performed.

The fluorescein dye also reappears in the patient urine, causing the urine to appear darker, and sometimes orange. It can also cause discoloration of the saliva. Fluorescein angiography is one of several health care applications of this dye, all of which have a risk of severe adverse effects, such as allergic responses.

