9. CLINICAL INVESTIGATION ASSESSMENTS

9.1 Clinical investigation flow chart(s) / table of clinical investigation procedures and assessments

There will be a consecutive ongoing recruitment of patients and healthy subjects attending routine follow-ups through the involved investigators in daily clinical practice at Department of Ophthalmology, Inselspital, Bern. Recruitment will last from October 2021 to November 2023. Patients, who fulfilled the indication of either SD-OCT or fluorescein angiography imaging for diagnosis of retinal/optic nerve disease will be included and additional imaging will be performed with the High-Res-OCT.

Subject	Initial imaging with High-Res-OCT
Healthy volunteers	X ₁
Patients with retinal/optic nerve disease	X ₁
X =mandatory imaging session. ¹ routine imaging with either SD-OCT, fundus photography or fluorescein angiography according to clinical routine	

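### The plan asks whether High-Res-OCT makes fluorescein angiography unnecessary, but no outcome reports the comparison with angiography separately and the secondary agreement outcome leaves it out

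*Combined protocol and SAP*

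**What the plan says.** **The question.** Section 3.1 gives the study aim as "whether High-Res OCT can reliably diagnose retinopathies thereby making more invasive investigations such as fluorescein angiography futile", together with diagnostic accuracy against conventional imaging. Section 4.1 repeats it and widens it to conventional methods: "thereby making more invasive investigations such as fluorescein angiography or conventional imaging methods futile".

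**The primary comparison.** Section 4.2 evaluates sensitivity and specificity "compared to conventional imaging methods, such as SD-OCT, fluorescein angiography". Section 5.1 asks for similar or higher values "as conventional imaging methods, such as SD-OCT, color fundus photography and fluorescein angiography". Sections 11.1 and 11.4 list the same modalities as examples. Section 9.2.1 refers to conventional modalities without naming angiography, and section 11.2 describes SD-OCT as the main comparator. Section 9.2.1 lists twelve types of change, each read as present or absent; neovascularization and ischemia are among them.

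**The secondary agreement outcome.** Section 5.2 has: "Evaluation whether pathological changes seen in SD-OCT or color fundus photography correlate with changes seen in High-Res-OCT". Sections 4.3 and 9.2.2 name the same two modalities. The exploratory outcome in section 5.3 concerns colour fundus photography.

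**Who has angiography.** The footnote to the table in section 9.1 reads "routine imaging with either SD-OCT, fundus photography or fluorescein angiography according to clinical routine". Section 12.1.2 records angiography where applicable. Section 8.1.2 describes it as "a technique for examining the circulation of the retina and choroid using a fluorescent dye".

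**The concern.** Whether an invasive, dye-based examination can be left out is the most consequential conclusion this trial could be asked to support. It needs results from participants who had both examinations, shown apart from the other comparators and for the findings that angiography is done to detect. The plan yields one pooled result, weighted towards SD-OCT by its own description, and an agreement outcome without angiography.

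The pooled analysis could be completed with very few angiograms and still look favourable, because most of the listed changes are structural and SD-OCT is the main comparator. A reader who starts from sections 3.1 and 4.1 could take that as evidence about angiography. An angiography comparison could be added later, since section 11.4.5 lets the analysis be adapted as questions arise, but a comparison chosen after the data are seen is weak support for a stated aim.

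**Working it through.** **1. Where angiography appears**

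| Place | Role of angiography |
|---|---|
| 3.1, 4.1 | Named in the study question |
| 4.2, 5.1, 11.1, 11.4 | An example within pooled conventional imaging |
| 9.2.1 | Not named |
| 11.2 | Not named; SD-OCT is the main comparator |
| 4.3, 5.2, 9.2.2 (agreement) | Left out |
| 5.3, 9.2.3 (exploratory) | Left out |
| 9.1, 12.1.2 | Done and recorded according to clinical routine |

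No outcome or analysis sets High-Res-OCT against angiography alone. Section 11.2 does speak of each modality's accuracy separately, but as an assumption (90%); no analysis by modality follows from it.

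**2. The plan's own figure.** The only sample size is 550, and no part of it is allotted to angiography. Inputs from section 11.2: accuracy 90% for both, 10-point margin, one-sided 5%, 90% power.

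n per group = 2 × 0.9 × 0.1 × (1.645 + 1.282)² / 0.10² = 0.18 × 8.57 / 0.01 ≈ 154.2, so 155, or 310 for two independent groups.

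The precision inputs in section 11.4.2 (0.03, 90%, prevalence 0.9) give 1.96² × 0.09 / 0.03² / 0.9 = 426.8, so 427. Neither gives 550. That is a separate matter, and this point does not depend on it.

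**3. What an angiography comparison could show.** The documents give neither the number of pairs nor the discordance (the proportion of pairs in which the two examinations disagree). Both are assumed here.

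- Pairs: 10%, 20% or 40% of the 450 patients, that is 45, 90 or 180.
- Discordance: 5%, 10% or 18%. The last is 2 × 0.9 × 0.1, two independent readings each 90% accurate. The maximum for two tests at 90% is 20%.
- Observed paired difference: zero.

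Distance from the observed difference to the one-sided 95% limit = 1.645 × √(discordance / pairs). For example, 1.645 × √(0.10 / 45) = 0.078.

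| Discordance | 45 pairs | 90 pairs | 180 pairs |
|---|---|---|---|
| 5% | 5.5 | 3.9 | 2.7 |
| 10% | 7.8 | 5.5 | 3.9 |
| 18% | 10.4 | 7.4 | 5.2 |

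Values are percentage points. Each side of a two-sided 95% interval is 1.96 / 1.645 = 1.19 times as long.

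With 45 pairs the distance reaches 10 points only when discordance is at least 45 × (0.10 / 1.645)² = 0.166, or about 16.6%.

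**The case against.** The strongest reply is that angiography is in the primary comparator. It is named in sections 4.2, 5.1, 11.1 and 11.4; the synopsis includes vascular abnormalities in the primary objective; and section 9.2.1 reads neovascularization and ischemia as separate binary outcomes. An indication for angiography is one of two routes into the study (section 9.1). Section 3.6 calls angiography routine for retinal vasculopathies, and diabetic retinopathy, vessel occlusion and hypertensive changes together make up 3 × 50 = 150 planned patients. All of this stands. Angiography data will exist, and a useful number of pairs is possible. It does not supply a separate result or a stated number of pairs.

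Four stronger readings are tempting, and the documents do not support them.

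- A reader might infer that detection of vascular findings goes untested against angiography. It is tested within the pool; it is not reported apart.
- A reader might infer that specificity against angiography has almost no data because healthy participants would seldom have one. Outcomes are per lesion, so a patient who had angiography and lacks a given lesion is a negative for that lesion. How often healthy participants have angiography is not stated.
- A reader might infer that the trial sets out to replace angiography. Sections 3.1 and 4.1 ask whether it becomes unnecessary, beside an accuracy aim.
- A reader might infer that a small subset, such as 45 pairs, could not exclude a 10-point deficit. At zero observed difference that is so only if discordance exceeds about 16.6%, which is near its maximum. The 10-point margin in section 11.2 is also a margin for accuracy, and a difference in detection proportion is not a difference in accuracy.

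**Conclusion.** The point holds as a mismatch between the question in sections 3.1 and 4.1 and the outcomes that are to answer it. As written, a favourable pooled result could not support a conclusion that angiography can be omitted. The plan's text alone establishes this.

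The size of the gap is uncertain. Under the assumptions above, the one-sided limit lies from 2.7 points (180 pairs, 5% discordance) to 10.4 points (45 pairs, 18% discordance) beyond an observed difference of zero. Whether the comparison would be informative depends on the number of pairs and on the discordance, and the plan gives neither. The table treats a single overall reading; results for single lesions will have their own discordance. The change is worth making because it is cheap and bears on the plan's own question. It does not call the pooled primary comparison into doubt.

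**What to change.** - In sections 4.3, 5.2 and 9.2.2, add fluorescein angiography to the agreement outcome. In participants who had both examinations, report High-Res-OCT against angiography separately, per lesion and at least for neovascularization and ischemia. Give the number of pairs, positive and negative agreement, and the paired difference in detection proportion with its 95% interval.
- In sections 3.1 and 4.1, state that any statement about omitting angiography rests on this comparison, and is not made if the interval is too wide to be informative.

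**Cost.** Wording in five sections and one extra table from images already taken, with no additional angiograms, visits or participants. The downside is that the aim about angiography may have to be stated more modestly if few pairs accrue.

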4.2 Primary Objective

The primary objective of this study is to evaluate the sensitivity and specificity to diagnose retinal morphological abnormalities with High-Resolution OCT compared to conventional imaging methods, such as SD-OCT, fluorescein angiography. The main parameters, which will be assessed are the presence of morphological abnormalities (such as but not limited to intraretinal or subretinal fluid, epiretinal membrane, substance defect, drusen, hyperreflective foci, atrophy, neovascularization, optic nerve, swelling, choroid abnormalities, scars, ischemia) within the macula and optic nerve head. The incidence (binary) and diagnostic accuracy of these morphological abnormalities will be assessed in High-Res-OCT and compared to conventional imaging methods such as SD-OCT.

4.3 Secondary Objectives

- Evaluation of the inter-reader reproducibility in healthy subjects with High-Res-OCT
- Evaluation whether pathological changes seen in SD-OCT or color fundus photography correlate with changes seen in High-Res-OCT. Here, a binary readout, i.e pathology present (yes/no) will be used.
- Subgroup analysis will be performed with patients suffering from diabetic retinopathy, artery and vein occlusion, retinal detachment, glaucoma, optic nerve neuropathy, hereditary retinal diseases, age related macular degeneration, retinal changes from arterial hypertension and uveitis.
- Evaluation of the intra-and inter-reader reproducibility in the diagnosis (binary) using High-Res-OCT
- Evaluation of the segmentation quality of the retinal layers using High-Res-OCT

4.4 Safety Objectives

As this is a CE certified device with minimal safety concerns no safety objectives are planned.

5. CLINICAL INVESTIGATION OUTCOMES

5.1 Primary Outcome

The primary outcome as measured on the individual patient-level is whether High-Resolution OCT has a similar or higher specificity and sensitivity to detect pathological changes in the retina/optic nerve as conventional imaging methods, such as SD-OCT, color fundus photography and fluorescein angiography. This will result in a binary outcome. Pathological morphological changes includes but are not limited to, intraretinal or subretinal fluid, epiretinal membrane, substance defect, drusen, hyperreflective foci, atrophy, neovascularization, optic nerve swelling, choroid abnormalities, scars, ischemia. Additionally, study participants will be asked to consent to prospective collection of clinical and demographic data, to correlate findings of High-Resolution OCT imaging to subsequent clinical course.

Ophthalmic diseases include, but are not limited to:

- Retinal vascular diseases
- Retinal detachment
- Hereditary retinal diseases/dystrophies
- Glaucoma
- Optic nerve neuropathy
- Inflammatory/infectious retinal diseases

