7.3 Assignment to investigation groups

The recruited participants will be assigned to the diagnostic categories mentioned at 6.1. or categorized as healthy. No randomization is planned.

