9.2.1 Assessment of primary outcome

The sensitivity and specificity of the High-Resolution OCT to diagnose the presence/absence of pathological changes in the retina/optic nerve in comparison to conventional imaging modalities will be assessed as a primary outcome. The following pathological changes will be assessed: intraretinal or subretinal fluid, pigment epithelial detachment, epiretinal membrane, substance defect, drusen, hyperreflective foci, atrophy, neovascularization, choroid abnormalities, scars, optic nerve swelling and ischemia. For each of these pathological changes a binary outcome will result. Additionally, study participants will be asked to consent to prospective collection of clinical and demographic data, to correlate findings of High-Res-OCT imaging to subsequent clinical course.

There is no need to be in a particular posture before the examination in order to obtain high quality images. The participants will be in a sitting position during the examination during approximately 30-60 seconds per eye. In case the measurement needs to be repeated, no waiting period will be necessary. A repeated measurement needs to be recorded in the CRF.

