11.2 Determination of Sample Size

The primary variable for this assessment is the ability to detect the presence of retinal structural abnormalities with High-Res-OCT in comparison to conventional ophthalmic imaging methods, mainly SD-OCT. This will result in a binary outcome. Assuming that the accuracy of each of these conventional imaging modalities separately is 90%, and there is truly no difference between the conventional imaging and High-Res-OCT (null hypothesis), then 550 patients are required to be 90% certain that the upper limit of a one-sided 95% confidence interval (or equivalently a 90% two-sided confidence interval) will exclude a difference in favor of the conventional imaging of more than 10%¹⁶.

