11.4.2 Primary Analysis

The results will be displayed using a receiver operating characteristic (ROC), or ROC curve. The curve is created by plotting the true positive rate (TPR) against the false positive rate (FPR) at various threshold settings. Here the required total sample size for estimating sensitivity (presence of the pathological changes within the scans) with respect to marginal error (0.03), sensitivity (90%) and the prevalence (0.9) of disease in target population would be approximately 550 subjects¹⁷. Depending on the results, precision and recall (PR) curves are also going to be computed, which are useful in case of distribution imbalance between two classes of a binary model, specifically if the true negative values are high, the latter not being taken into account in the calculation³⁰. Precision (Y-axis) is referred as the positive predictive value and recall (X-axis) as sensitivity. A high precision value means that the tested classifier/device provides accurate results, while high recall indicates that the majority of all positive samples were detected. The possible AUC value ranges from 0.5 (discriminative performance equal to chance) to 1.00 (perfect discriminative performance). The primary analysis will be done using

Python 3 and its open-source package Scikit-learn v0.20.3.

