12.1.2 Specification of source data and source documents

Source data will be available at the site to document the existence of the investigation subjects. Source data will include the original documents relating to the investigation, as well as the medical treatment and medical history of the subject.

The source documents include:

- Demographic form: Study ID, study eye, personal information (year of birth, age, sex), eye anamnesis (diagnosis, date of diagnosis, recurrences). Data will be entered electronically in REDcap.
- Examination form (data from both eyes): visit date and if applicable, visual acuity, SD-OCT; FA, ICG, FAF plus additional information if required (correction). Data will be entered electronically in REDcap.
- Informed consent form; stored in a locked cupboard.

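### The primary outcome is sensitivity and specificity, but the plan names no reference standard: disease status is only implied at patient level, and no usable reference is given for each pathological change

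*Combined protocol and SAP*

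**What the plan says.** Section 5.1 sets the primary outcome, at patient level, as "whether High-Resolution OCT has a similar or higher specificity and sensitivity to detect pathological changes in the retina/optic nerve as conventional imaging methods". Section 9.2.1 lists the changes to be read and adds: "For each of these pathological changes a binary outcome will result". The primary analysis (11.4.2) is a curve made by "plotting the true positive rate (TPR) against the false positive rate (FPR) at various threshold settings".

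What the plan offers that could serve as truth:

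- **Conventional imaging.** Sections 3.6 and 8.1.2 present it as the comparator. Section 11.2 sizes the study thus: "Assuming that the accuracy of each of these conventional imaging modalities separately is 90" per cent. The footnote to the table in 9.1 specifies "routine imaging with either SD-OCT, fundus photography or fluorescein angiography according to clinical routine".
- **Disease status.** Section 7.3: "The recruited participants will be assigned to the diagnostic categories mentioned at 6.1. or categorized as healthy". The demographic form in 12.1.2 holds "Study ID, study eye, personal information (year of birth, age, sex), eye anamnesis (diagnosis, date of diagnosis, recurrences". Section 11.4.2 uses a disease prevalence of 0.9, and 3.8 adds healthy subjects in order to validate the method.
- **Readers.** Three readers appear in 9.2.2, for reproducibility only, with no consensus or adjudication.
- **Later clinical course.** Sections 5.1, 6.1 and 9.2.1 plan to correlate findings with it, while 6.1 and 9.3 use clinical records only until the visit.

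A secondary outcome (5.2) is "Evaluation whether pathological changes seen in SD-OCT or color fundus photography correlate with changes seen in High-Res-OCT".

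**The concern.** Sensitivity is the proportion of truly affected subjects who are read as positive; specificity is the matching proportion among the truly unaffected. Without a rule for who is truly affected, neither can be calculated, and no point on a true/false positive curve is defined. None of the sections above supplies that rule.

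The choice can change the conclusion. The rationale for the device is finer axial resolution (3 versus 7 µm, section 3.1). If the comparator became the truth by default, real findings visible only on High-Res-OCT would be counted as false positives. If disease status is the truth, the result is different. Leaving this open also allows the reference to be chosen after the data are seen; section 11.4.5 permits the analysis to be adapted during the work, although deviations must be described and justified.

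**Working it through.** **1. Can each candidate serve as the reference?**

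- Conventional imaging: no. Scored against itself it has 100% sensitivity and specificity by construction, so High-Res-OCT could never be shown to be higher, which 5.1 allows for. It would also contradict the 90% accuracy assumed in 11.2, and it is not the same test in every subject (9.1).
- Diagnosis/healthy category: possible at patient level, and recorded, but not named as the reference. It cannot say whether, for example, drusen or subretinal fluid is truly present, which the separate outcomes in 9.2.1 would need.
- Readers: no consensus truth is planned.
- Later course: not called a reference, and in conflict with the limit on records in 6.1 and 9.3.

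**2. The plan's own figure.** The precision calculation in 11.4.2 presupposes a known disease state. With its inputs and 95% confidence, 1.96² × 0.9 × 0.1 / 0.03² = 384.2, so 385 diseased; 384.2 / 0.9 = 426.8, so 427 subjects. The stated figure is about 550. That discrepancy is a separate matter and nothing below depends on it.

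**3. Illustration: conventional imaging taken as truth.** Inputs: 450 diseased and 100 healthy (6.1); comparator sensitivity 0.90 and specificity 0.90 to 1.00 (my reading of the plan's 90%); a perfect High-Res-OCT.

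Apparent specificity = (healthy, comparator negative) / (all comparator negative).

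- Comparator specificity 0.90: 90 / (90 + 45) = 0.667.
- Comparator specificity 1.00: 100 / (100 + 45) = 0.690.
- At the stated prevalence of 0.9 (495 and 55): 49.5 / 99 = 0.500 to 55 / 104.5 = 0.526.

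A High-Res-OCT exactly as accurate as the comparator (both 0.90/0.90, independent errors) would show a specificity of (90 × 0.9 + 45 × 0.1) / 135 = 85.5 / 135 = 0.633.

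**4. Disease status taken as truth: power.** Paired difference, margin 0.10 and one-sided 5% (11.2), both devices assumed at 0.90, error correlation ρ assumed from 0 to 0.5.

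Discordance d = 2 × 0.9 × 0.1 × (1 − ρ); power = Φ(0.10 / √(d/n) − 1.645).

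| Measure | n | ρ = 0 | ρ = 0.25 | ρ = 0.5 |
|---|---|---|---|---|
| Sensitivity | 450 | >0.999 | >0.999 | >0.999 |
| Specificity | 100 | 0.762 | 0.859 | 0.954 |

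The plan's 90% power for specificity needs d ≤ 100 × 0.10² / (1.645 + 1.282)² = 0.1168, so ρ ≥ 1 − 0.1168/0.18 = 0.35.

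Not every subject need have SD-OCT (9.1), and the number who will is not given. If it were 225 diseased, sensitivity power is still 0.971 at ρ = 0. If it were 50 healthy, specificity power is 0.509 to 0.762 over ρ = 0 to 0.5.

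**5. What the disease label does to real extra findings.** Suppose High-Res-OCT alone shows a real incidental change in 7 of 100 healthy subjects, with no other discordance. The upper limit of the specificity loss is 0.07 + 1.645 × √(0.07 × 0.93 / 100) = 0.112, or 11.2 points. The device fails the 10-point margin although its readings are right.

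**The case against.** The best defence is that the patient-level gap is mainly one of naming. The 0.9 prevalence in 11.4.2, the healthy group in 3.8, the comparison of patients with healthy subjects in 9.2.2 and the categories in 7.3 all point to disease status. That stands, and it limits the point: a reader might infer that the plan has no truth anywhere, and the documents do not support that. Later clinical course is also mentioned in both primary-outcome sections (5.1, 9.2.1). It is not called a reference and conflicts with the limit on records, so it is an unresolved contradiction rather than a solution.

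A second objection is that disease status is itself an imperfect reference. This stands too. All subjects, healthy ones included, come from those requiring conventional imaging (7.1), and nothing makes the diagnosis independent of that imaging. One might suppose that a common label puts the two devices on an equal footing; it may in fact favour the comparator, and step 5 shows that it shares part of the harm of using the comparator as truth. The label also measures disease rather than the changes listed in 9.2.1. These are limits of the repair. They do not remove the need to name a reference.

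Thirdly, the case report form and device manuals are separate appendices that were not supplied and may say more. The protocol should still define its own primary outcome.

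**Conclusion.** The point holds and must be fixed before analysis: the primary outcome, as written, has no designated reference standard. At patient level the reference is implied but not declared; for each pathological change no usable one is given.

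The specificity of 0.67 to 0.69 is conditional on conventional imaging being used as truth and on the assumed accuracy. A reader might take it as the bias this study will have. The documents do not support that, because they never say that conventional imaging will be the truth, and the 90% assumption argues against it. What the figure shows is that the undeclared choice is large enough to decide the result.

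With disease status as the reference, sensitivity is amply powered. Specificity, with at most 100 healthy subjects, has 76% to 95% power at error correlations of 0 to 0.5 if both devices are at 0.90, and less if some healthy subjects lack SD-OCT.

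**What to change.** In 5.1, 9.2.1 and 11.4.2:

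- State that conventional imaging is not the truth. Score High-Res-OCT and SD-OCT at patient level against one common reference, the 7.3 diagnosis/healthy category, fixed before study images are read, in subjects with both tests.
- Give one rule for a positive read (for example, at least one listed change), and use the study eye already recorded under 12.1.2.
- Report paired differences in sensitivity (diseased) and specificity (healthy) with one-sided 95% limits against the 10-point margin. State that both must meet it before equivalent or better accuracy is claimed.
- Report one sensitivity/specificity point in place of the ROC curve, unless a graded score is read.
- For each change, and for fundus photography and angiography in those imaged, report paired detection and positive/negative agreement with confidence intervals. Claim no sensitivity or specificity there unless a reference independent of both devices exists.
- Reconcile the statements on later clinical course (5.1, 6.1, 9.2.1) with those limiting records to the visit (6.1, 9.3).

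**Cost and limits to state.** The label and study eye are already recorded, so no new imaging is needed, but SD-OCT images must be read to the same rule, and a protocol amendment is required. The label may favour the comparator. A real incidental change in a healthy subject counts against the device that shows it, and a diagnosed patient with no listed change is a miss for both. Specificity rests on at most 100 subjects. Claims for single changes and against angiography become narrower than sections 4.1 and 4.2 intend.
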